### 8.5.2 Time and rate to first related TEAE with toxicity of grade 3 or higher

Time to first related TEAE with toxicity of grade 3 or higher acc. CTCAE v5.0 criteria as defined in section 7.7.13 will be evaluated using Kaplan-Meier method based on the SES. The estimates

obtained are invariably expressed graphically. Median survival time with two-sided 95% confidence intervals (CI) using the complementary log-log transformation method will be tabulated. Survival rate before week ■ (in ■■■■■) and week ■ (in ■■■■■) with exact two-sided 95% confidence interval using the Clopper-Pearson method will be provided.

Table	
14.7.6	Time and rate to first related TEAE with toxicity of grade 3 or higher
Figures	
14.7.6	Time to first related TEAE with toxicity of grade 3 or higher

### 8.5.3 Extent of exposure

Duration of treatment (see 7.7.3), treatment compliance, total dose and dose intensity (see 6.2.3) will be summarized with descriptive statistics overall. Dose intensity will be summarized by cycle and by overall mean in a subject level. Dose modifications will be listed separately.

Table	
14.8.1	Extent of exposure
Listing	
16.8.1	Extent of exposure
16.8.2	Dose modifications

### 8.5.4 Other safety assessments

Clinical chemistry, vital signs, Automated complete blood count and BM Cytology Assessment (see 6.2.3) will be summarized descriptively by visit (using the visit labelling from the SoA (see 2.4)) for the original data as well as for the difference to baseline (as defined in 7.7.1). Patients with laboratory values outside of the normal reference range at any postbaseline assessment will be listed.

Table	
14.9.1	Clinical chemistry
14.9.2	Vital signs
14.9.3	Automated complete blood count
14.9.4.1	BM Cytology Assessment (continuous)
14.9.4.2	BM Cytology Assessment (categorical)
Listing	
16.9.1	Clinical chemistry

16.9.2	Vital signs
16.9.3	Automated complete blood count
16.9.4	BM Cytology Assessment
16.9.5	CBC with differential
16.9.6	Cytogenetic Analysis
16.9.7	Physical examination

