8.1.3 Treatment period

The subject will start treatment upon confirmation of eligibility. The subject must start treatment within [REDACTED] of signing the ICF. If screening assessments are performed within 72 hours of C1D1, serum chemistry laboratory assessments and physical examinations need not be repeated at C1D1 with the exception of automated CBC.

If subject completed the QoL EORTC QLQ-C30 questionnaire at Screening within 2 weeks of C1D1, it does not have to be repeated at C1D1. If performed on C1D1, it should be completed prior to IMP administration.

On dosing days, local laboratory levels should be assessed prior to each IMP administration to ensure dose modification rules are followed as outlined in section 7.3 Dose modification guidelines.

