8.1.7 Dose delays

In case of dosing delays, the visit schedule will be adjusted. Visits indicating dosing will only be performed if the patient is ready to receive their next dose. These visits will be postponed in case of dosing delays (section 7.3). Visits without dosing of subjects (for example [REDACTED] in responding patients with <5% BM blasts) should be performed two (2) weeks \pm 3d after the preceding dosing visit irrespective of dosing delays.

During the time period of dose delay, the following assessments/procedures should be performed:

- If dose delay is due to a laboratory or vital signs abnormality, the assessment that was the reason for the dose delay should be repeated at least on weekly basis.
- If dose delay is due to an AE, perform hematology and serum chemistry at least every 2 weeks thereafter and before next dose administration.

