8.1.8 Unscheduled visits

Should it become necessary to repeat an evaluation (e.g., laboratory tests or vital signs), the results of the repeat evaluation should be entered as an additional unscheduled visit in the eCRF.

Refer to the eCRF completion guidelines for detailed instructions related to eCRF data entry.

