### 8.8.1 Unscheduled Visits

Unscheduled visits may be performed, as necessary, to ensure the safety and well-being of subjects. Data from these visits will only be included in the subject listings but not in the statistical analysis tables and figures with the following exceptions:

- AEs
- Concomitant medications

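### Repeat blood counts taken during a laboratory-driven dose delay reach listings only, and no worst-grade or shift laboratory table is planned to summarise them

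*SAP*

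**What the plan says.** Four rules bear on this point.

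- **Timing of dosing visits and tests.** Protocol 8.1.3: "On dosing days, local laboratory levels should be assessed prior to each IMP administration to ensure dose modification rules are followed". Protocol 8.1.7, on delays: "Visits indicating dosing will only be performed if the patient is ready to receive their next dose". Visits without dosing, by contrast, take place two weeks "after the preceding dosing visit irrespective of dosing delays".
- **Tests during a delay.** Protocol 8.1.7: when a laboratory or vital-sign abnormality causes the delay, "the assessment that was the reason for the dose delay should be repeated at least on weekly basis". For the other case: "If dose delay is due to an AE, perform hematology and serum chemistry at least every 2 weeks thereafter and before next dose administration".
- **Filing of repeats.** Protocol 8.1.8: "the results of the repeat evaluation should be entered as an additional unscheduled visit in the eCRF". The same section refers sites to the eCRF completion guidelines for detailed entry instructions.
- **Analysis.** SAP 8.8.1, on unscheduled visits: "Data from these visits will only be included in the subject listings but not in the statistical analysis tables and figures". The only exceptions are adverse events and concomitant medications. SAP 8.5.4 states that chemistry, vital signs, automated blood count and marrow cytology "will be summarized descriptively by visit (using the visit labelling from the SoA (see 2.4)) for the original data" and as differences from baseline.

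The laboratory tables in SAP 8.5.4 and Appendix 11.1 are 14.9.1, 14.9.3, 14.9.4.1 and 14.9.4.2. None is a CTCAE-grade, worst-value or shift table. SAP 8.5.4 also lists patients with any out-of-range value after baseline.

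**The concern.** Protocol 7.2.2.1 names cytopenias as the primary dose-limiting toxicities of imetelstat and ties their frequency and severity to dose intensity. Protocol 1.3.1 accepts that the more frequent dosing now in use could aggravate neutropenia. A reader of the report will want to know how many patients in each cohort reached Grade 3 or 4 neutropenia or thrombocytopenia by laboratory value.

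The planned laboratory tables cannot answer that. They are organised by scheduled visit label, and the counts collected while a dose is on hold, when toxicity is most likely to be present, are confined to listings. If a count falls further after the hold begins, its lowest value appears in no laboratory table.

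**Working it through.** The documents give no figure for this point to reproduce, so the check is a trace of the rules, a count on the schedule, and a count per hold.

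**1. The trace.** A laboratory-driven delay requires a repeat at least weekly (Protocol 8.1.7). The repeat is entered as an unscheduled visit (Protocol 8.1.8). Unscheduled laboratory data go to listings only (SAP 8.8.1). The laboratory tables are by schedule label (SAP 8.5.4). No other laboratory table picks the value up (SAP 11.1).

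**2. Which scheduled blood counts coincide with dosing.** Source: SAP 2.4 and Protocol section VII. Part 1 has 11 columns. Response assessment is marked in columns 6 and 10, which SAP 8.3 calls visits 5 and 9, so column 1 is screening and columns 2 to 11 are V1 to V10.

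| Schedule part | Columns with automated blood count | Of these, dosing visits |
|---|---|---|
| Part 1, V2–V9 | 8 | 8 |
| Part 1, V10 | 1 | only for responders with marrow blasts of 5% or more |
| Part 2a | 9 | 5 (4 non-dosing) |
| Part 2b | 9 | 9 |
| Part 3 | 3 of 5 | 0 |

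Chemistry within V2–V9 is marked at V3, V5, V7 and V9, so all 4 fall on dosing visits. Part 2c has no automated-count or chemistry row.

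In the main treatment phase, then, every scheduled count from V2 to V9 belongs to a visit that is held only once the patient can be dosed. V10 for most patients who attend it, four Part 2a columns and Part 3 do supply counts that are not tied to dosing. The table covers the current schedule, which applies to Cohort 2. Cohort 1 was dosed once per cycle (SAP 2.7), and its schedule is not shown.

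**3. Untabulated results per laboratory-driven hold.** Let the patient restart on day *d*, with repeats every 7 days, the stated minimum. The pre-dose value on day *d* belongs to the postponed dosing visit and is tabulated. Then

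untabulated repeats = *d*/7 − 1, plus 1 if the triggering value is also filed as unscheduled.

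| Restart day *d* | Trigger filed under scheduled visit | Trigger filed as unscheduled |
|---|---|---|
| 7 | 7/7 − 1 = 0 | 0 + 1 = 1 |
| 14 | 14/7 − 1 = 1 | 1 + 1 = 2 |
| 21 | 21/7 − 1 = 2 | 2 + 1 = 3 |
| 28 | 28/7 − 1 = 3 | 3 + 1 = 4 |

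The restart days are assumptions that span the 28-day limit in Protocol 7.1. The counts are minima, because testing may be more frequent than weekly.

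**4. AE-driven holds.** The protocol says the tests are performed, not repeated, so filing them as unscheduled is an inference. If it is right, the untabulated results at the two-week minimum are the 14-day points before day *d*: 0, 0, 1 and 1 for the same restart days, or 1, 1, 2 and 2 with an unscheduled triggering value.

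**5. Effect on the visit summaries.** If the triggering value stays under the scheduled visit, tables 14.9.1 and 14.9.3 keep it and the visit summaries are unaffected; only later repeats are missing. If it is filed as unscheduled, the label carries the value at which dosing resumed, and the summary for that visit leans towards recovered counts. The size cannot be derived, because the haematologic hold thresholds are not available in the public documents.

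**The case against.** The strongest reply is that any distortion of the visit tables depends on a filing rule that the public documents do not show, and that the visible text partly favours the harmless case. Protocol 7.1 applies the delay rules to Grade 3 or 4 toxicity present when the next dose is due. Protocol 8.1.3 has the laboratory values taken before each dose. Protocol 8.1.8 sends only repeats to an unscheduled visit, and the first low value is not a repeat. The postponement of dosing visits in Protocol 8.1.7 points the other way. This part of the reply stands: the direction is unsettled, and the eCRF completion guidelines may already settle it.

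The reply also has a case on mitigation. Out-of-range patients are listed, as are dose modifications (16.8.2). Adverse events are exempt from the SAP 8.8.1 exclusion, so a reported cytopenia reaches the graded table 14.7.3, table 14.7.4 if early, and table 14.7.6 if related and Grade 3 or higher. Protocol 9.1.1 treats a condition that worsens after consent as an adverse event, so a baseline cytopenia is no exemption, and values that stopped a dose are the ones least likely to go unreported. This also stands in part. Reporting still passes through the investigator's judgement of clinical significance (Protocol 9.3), in patients who all enter with at least one cytopenia (Protocol 6.3). A laboratory-grade table does not depend on that judgement.

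Finally, Protocol 10.9.4 asks only for descriptive summaries and an out-of-range listing, and the SAP supplies both. That is correct: there is no departure from the protocol. Protocol 10.9 sets summary statistics as a minimum, however, and leaves full details to the SAP.

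**Conclusion.** The point holds as a minor summary gap. Repeat laboratory values from a laboratory-driven delay reach no laboratory table, and nothing planned reports the worst grade by cohort. At the weekly minimum this leaves 0 to 3 untabulated repeats per hold with restart by day 28, or 1 to 4 results if the triggering value is also unscheduled.

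A reader might infer more than this, and the documents do not support it:

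- *That the by-visit tables necessarily understate cytopenia.* They do so only if the triggering value is filed as unscheduled. Otherwise the effect on them is zero.
- *That severe cytopenia is hidden or data are lost.* The values are in the listings, and reported events are in the graded adverse-event tables. Part 3 counts can also bring back patients who never restart, where the visit has more than 5 observations (SAP 8.1).
- *That the comparison of regimens is biased.* The visit count applies to the current schedule only, and Cohort 1's schedule is not shown.

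All analyses are exploratory (Protocol 10.1), and no planned conclusion fails. Confidence is medium, because the filing instructions and hold thresholds cannot be seen.

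**What to change.** Add one table to SAP 8.5.4, by cohort on the Safety Evaluation Set: a shift from baseline to worst post-baseline CTCAE v5.0 grade for neutrophils, platelets, haemoglobin, ALT, AST and bilirubin, using every post-dose value, scheduled or unscheduled. The shift form is needed because every patient enters with at least one cytopenia. In SAP 8.8.1, add laboratory values for this table to the exceptions.

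It would also help to state in the SAP which visit carries the value that triggered a delay, and to footnote the visit tables to say that dosing visits go ahead only when the patient can be dosed. These two additions alone would not close the gap.

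The cost is one extra table with its programming and a few lines of SAP text. The data are already collected and listed, and no new tests are needed.

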## 8.6 Other Endpoints

Transfusions as defined under section 6.2.3 will be summarized on a subject level based on the FAS using the methods described in 8.1 by transfusion type and differentiating by within 16 weeks before treatment and after first dose transfusions. Non RBC or Platelet transfusions will only be listed.

All parameters will be listed for all available visits (i.e., screening, FU/ET visit and extension treatment phase included) using the visit labelling from the SoA (see 2.4).

All results will be presented by treatment cohort (see 2.7).

Table	
14.10.1	Transfusion history by type of transfusion
Listing	
16.10.1	Transfusion history by type of transfusion

## 8.7 Further parameters

ECOG Performance Status as defined in section 6.2.3 will be listed including all available visits (i.e., screening, FU/ET visit and extension treatment phase included) using the visit labelling from the SoA (see 2.4).

Listing	
16.11.1	ECOG Performance Status

## 8.8 Special Analytical Issues

If multiple analysis sets contain the same number of subjects, the analysis will only be performed for one of these analysis sets. In tables and figures, both analysis sets will be referenced, if applicable.

### 8.8.1 Unscheduled Visits

Unscheduled visits may be performed, as necessary, to ensure the safety and well-being of subjects. Data from these visits will only be included in the subject listings but not in the statistical analysis tables and figures with the following exceptions:

- AEs
- Concomitant medications

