¹¹ Can be done at patient's general practitioner practice at investigator's discretion (for non-treatment visits only)

¹² If a patient is responding to imetelstat and continues beyond ■, each disease assessment should determine whether treatment with imetelstat is given every ■ weeks (responding with ≥5% BM blasts) or every ■ weeks (responding with <5% BM blasts).

¹³ Response assessment every 3 months (when BM cytomorphology is carried out)

Telomere length & telomerase profiling at central laboratories									
Study-specific biomaterial collection			x						
Local assessments									
CBC with differential (local)			x					x ¹⁴	x ¹⁵
PB blast assessment (local)	x		x		x		x	x ¹⁴	x ¹⁵
BM cytology assessment (local) ¹⁰			x					x ¹⁴	x ¹⁵
Serum chemistry (local)	x		x		x		x	x	x
Automated CBC (local)	x	x ¹¹	x	x ¹¹	x	x ¹¹	x	x	x
Cytogenetics (local)			x					x	

¹⁴ Only to be carried out if the last assessment is more than 14d apart

¹⁵ BM / CBC assessment every 3 months and at every timepoint of suspected progression starting ■ weeks after last morphology assessment at ■

Part 2b – extension treatment phase, from cycle 5 until loss of response / disease progression (**responders with BM blasts $\geq 5\%$ only**)

VISIT NO.									
Study Day ($\pm 3d$)									
Study Week									
Cycle									
Informed consent									
In- / exclusion criteria ³									
MDS/AML related medical history									
Concomitant MDS/AML specific medication	x		x		x		x		x
Physical examination, vitals	x	x	x	x	x	x	x	x	x
ECOG performance status									
BMI			x						
Pregnancy test ⁴	x		x		x		x		x
Imetelstat administration ⁵ and drug account	x	x	x ⁶	x	x	x	x	x	x ¹²
Toxicity/AE assessment	x	x	x	x	x	x	x	x	x
Quality of life (QoL, EORTC QLQ-C30)	x		x		x		x	x	x
LOCAL LABORATORY: Response assessment ⁸			x					x	x ¹³
Central assessments / correlative analyses (EU: Leipzig, AUS: QIMRB, Brisbane)									
Bone marrow aspiration (5 mL sodium heparinized in separate tubes for central assessments)			x						
Peripheral blood sampling for central assessments (10 mL sodium heparinized blood in separate tubes for central assessments)			x						
Genetic profiling (NGS) at central laboratories									
MRD analyses at central laboratories			x						
Telomere length & telomerase profiling at central laboratories									
Study-specific biomaterial collection			x						
Local assessments									
CBC with differential (local)			x					x ¹⁴	x ¹⁵
PB blast assessment (local)	x		x		x		x	x ¹⁴	x ¹⁵

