8.1.6 Extension Phase of the Treatment Period: [REDACTED]

Subjects who meet the criteria to remain on treatment after completion of the [REDACTED] disease assessment and have BM blasts $\geq 5\%$ may continue dosing on [REDACTED] of each [REDACTED] treatment cycle in the extension phase of the treatment period. Subjects who meet the criteria to remain on treatment after completion of the [REDACTED] disease assessment and have BM blasts $< 5\%$ may continue dosing on [REDACTED] (only) of each [REDACTED] treatment cycle in the extension phase of the treatment period.

Treatment will continue until the subject experiences unacceptable toxicities, disease progression per the combined response criteria used in this trial (Appendix III, section 16.3), withdraws consent, or meets any other discontinuation criteria (section 7.7).

BM and PB samples will be collected (e.g., for cytomorphology, cytogenetic analysis) and the disease assessment will be repeated by the investigator at [REDACTED] and at [REDACTED] in the extension phase. Patients showing a benefit from the therapy in [REDACTED] can continue treatment with the IMP. Beyond [REDACTED], disease assessments (including cytomorphology and therefore collection of BM and PB samples) will be carried out every 3 months and at every timepoint of suspected progression starting [REDACTED] after the last disease assessment in [REDACTED]. Also see VII Schedule of assessments and procedures, part 2).

Each BM assessment [REDACTED] months thereafter) should also be used to determine the frequency of treatment with imetelstat until the next disease assessment: every [REDACTED] weeks (if BM blasts are $\geq 5\%$) or every [REDACTED] weeks (if BM blasts are $< 5\%$).

A BM biopsy is to be collected only when adequate aspirate is not attainable or if the BM aspirate shows fewer than 5% bone marrow blasts. Whenever a BM sample is collected, both BM and PB smears are to be prepared for the cytomorphology assessment. Refer to the Laboratory Manual for additional information.

In addition, information related to all transfusions received during the treatment period (including those received outside the trial site) should be available prior to completion of each

disease assessment.

For subjects to continue treatment in the extension phase of the treatment period, each disease assessment should confirm continued clinical benefit and absence of disease progression per the combined criteria used in this trial (Appendix III).

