#### 7.7.6 Progression-free-survival

Progression-free-survival (PFS) will be defined as the duration of time from time of treatment to time of progression or death, whichever occurs first. A subject who has neither progressed (defined as first time having Progressive disease (PD) or Progression or relapse after HI on response assessment) nor died will be censored on the date of the last observation. Therefore:

In case there was a progression or death:

PFS [days] = min(date of progression/death) – Drug administration date in Visit [REDACTED] +1

Otherwise, censoring date will be:

PFS [days] = date of last observation – Drug administration date in Visit [REDACTED] +1

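### SAP 8.8.1 conflicts with the PFS and DoR derivations: read literally, it drops any progression recorded at an unscheduled visit, which biases both endpoints upward

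*SAP*

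**What the plan says.** - **SAP 8.8.1** on unscheduled visits: "Data from these visits will only be included in the subject listings but not in the statistical analysis tables and figures". Two exceptions follow, adverse events and "Concomitant medications". Response assessments, marrow results, blood counts and transfusions are not among them.
- **SAP 7.7.6** defines progression for PFS as "first time having Progressive disease (PD) or Progression or relapse after HI on response assessment". Death is also an event. Everyone else is censored at the last observation.
- **SAP 7.7.7** ends DoR at the first documented progression and otherwise censors at the last response assessment. Death is not a DoR event. Neither 7.7.6 nor 7.7.7 limits which visits count.
- **SAP 8.4.2 and 8.4.3** report PFS in Table and Figure 14.6.2 and DoR in Table 14.6.3, so the wording of 8.8.1 reaches both.
- **Protocol 8.1.6** says that, after a redacted visit in the extension phase, disease assessments "will be carried out every 3 months and at every timepoint of suspected progression". Footnote 15 of the assessment schedule has the same requirement: "BM / CBC assessment every 3 months and at every timepoint of suspected progression starting" (the starting week is redacted).
- **Protocol 8.1.8** says that when an evaluation has to be repeated, "the results of the repeat evaluation should be entered as an additional unscheduled visit in the eCRF".
- **Schedule Part 3** (end of treatment and follow-up) has no row for response assessment or local marrow cytology.

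**The concern.** An assessment prompted by suspected progression happens when the patient deteriorates, not on a calendar date. If the site enters it under an unscheduled visit label, 8.8.1 sends the result to the listings and keeps it out of the PFS and DoR outputs. The patients affected are those who have just progressed, so the loss is not random: events are removed and progression-free time is added.

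Two programmers could also follow this SAP correctly and obtain different numbers of PFS events, one by applying 8.8.1 to every output and the other by letting 7.7.6 and 7.7.7 stand alone. In a small single-arm study reported by cohort, a few events can move a Kaplan-Meier curve visibly.

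**Working it through.** The plan gives no figure on this point, so there is none to reproduce. The check is to follow one patient through the rules and then ask what size could follow.

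**Tracing a patient whose progression is recorded at an unscheduled visit**

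1. The progression is a response-assessment result and not one of the two exceptions. Under 8.8.1 it is listed only.
2. Treatment stops and the patient moves to Part 3, which has no response assessment. End-of-treatment marrow is sampled, for the central laboratories, only if more than 90 days have passed since the previous marrow procedure (footnote 22). A recent off-schedule marrow therefore switches it off.
3. Part 3 does record state of condition and survival, and protocol 7.7 lists disease progression as a reason for discontinuation. SAP 7.7.6 uses neither field; it takes progression from the response assessment.
4. PFS: the patient has an event only if death is recorded, dated at death. Otherwise the patient is censored at the last observation, which may fall in follow-up after the progression. Both outcomes lengthen PFS.
5. DoR: death is not an event, so the patient is censored at the last response assessment that counts. The Kaplan-Meier curve rises. SAP 8.4.3 also mentions plain descriptive summaries; the upward direction holds for the Kaplan-Meier analysis.
6. BOR: a patient who already has a response keeps it. The result changes only where the dropped assessment was the only one, or the one that showed the best response.

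**Size, as an illustration only**

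Let f be the share of progressions entered as unscheduled (not in the documents) and m the median time from progression to death (also not in the documents). Assume exponential survival after progression, follow-up of 3 months (protocol 7.7), and that every patient progresses before dying. Then:

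share of patients losing their PFS event = f × 0.5^(3 months / m)

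| m | 0.5^(3 months / m) | f = 0.25 | f = 0.50 | f = 0.75 |
|---|---|---|---|---|
| 10 weeks (assumed; 3 months = 13 weeks) | 0.5^1.30 = 0.41 | 10% | 20% | 30% |
| 4 months | 0.5^0.75 = 0.59 | 15% | 30% | 45% |
| 5.6 months | 0.5^0.54 = 0.69 | 17% | 34% | 52% |

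The 4 and 5.6 months are the median survival range that protocol 1.1.1 gives for higher-risk MDS after HMA failure. They are borrowed as a range and are not survival after progression on imetelstat. Off-schedule progressions that do not lose their event are dated at death instead. If f = 0, nothing is lost.

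A simulation of 200,000 patients (m = 10 weeks; median time to progression 8, 13 or 20 weeks; f = 0.25, 0.50 or 0.75) shows the same direction. With a 13-week median, PFS at the week-17 visit is 43% when all progressions count, against 50%, 58% and 67% when the off-schedule ones are dropped. Over all settings the rise is about 6 to 30 percentage points. These settings place off-schedule progressions before week 17, where the protocol does not require assessment on suspicion, so they show direction and not expected size.

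**The case against.** **Suspected-progression assessments may not be unscheduled.** Footnote 15 attaches them to marked cells of the extension schedule, and protocol 8.1.8 uses the term for repeated evaluations such as laboratory tests and vital signs. This stands. A reader might infer that every assessment made on suspicion is entered as unscheduled; the documents do not say so, and the eCRF labels are not available. The point is therefore conditional. The escape is also only partial: the primary-phase schedule has response assessments at weeks 9 and 17 and no column for one made on suspicion.

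**A specific derivation normally overrides a general display rule.** On that reading nothing is lost. It is a sensible reading, but the SAP does not state it, and the exceptions in 8.8.1 are a closed list.

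**Few patients are reached.** The suspicion clause applies in the extension phase, and the SAP history reports no responders at the interim. This limits the likely size. It does not empty the point: PFS covers the whole full analysis set, and 7.7.7 starts DoR at stable disease as well as at response.

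**Median PFS would not simply be inflated by half.** A reader might reason that losing one third of events multiplies the median by 1/(1 − 1/3) = 1.5. That requires constant hazard, no deaths and an invented share. Death is a PFS event, and survival in this population is short.

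**Laboratory tables.** During a dose delay for a laboratory or vital-sign abnormality, "the assessment that was the reason for the dose delay should be repeated at least on weekly basis". A reader might infer that the by-visit tables omit the worst counts. Nothing shows that these repeats are the lowest values; they may equally track recovery. Clinically relevant cytopenias can still enter as adverse events, and out-of-range values are listed. By-visit tables limited to scheduled visits are conventional.

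**Conclusion.** The conflict between SAP 8.8.1 and SAP 7.7.6 and 7.7.7 is real, and no order of precedence is stated. Applied literally, 8.8.1 drops any progression, or relapse after hematologic improvement, recorded at an unscheduled visit. The follow-up schedule does not recover it. The bias runs one way: upward for PFS and for Kaplan-Meier DoR.

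The size cannot be derived from the documents. It rests on the share of progressions entered under an unscheduled label, which could be zero, and on survival after progression. The figures above are illustrations under those assumptions.

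The scope is narrow. BOR is affected only marginally. Deaths still count for OS, and only a last-alive date could shift. Transfusion units after first dose are summed by date (SAP 7.7.2), and the primary endpoint uses the investigator's responder item in the eCRF (SAP 6.2.1); neither depends on 8.8.1 in any material way. Protocol 10.1 makes all analyses exploratory, and no decision rule rests on PFS or DoR. This should be fixed, but it does not undermine the study.

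**What to change.** Amend SAP 8.8.1 in two sentences:

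1. The exclusion of unscheduled visits applies only to summary tables presented by visit.
2. PFS, DoR, BOR and the last-alive date for OS use all response assessments, together with the marrow, blood-count and transfusion data behind them, scheduled or unscheduled, at their actual dates.

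It would also help to state in the eCRF completion guidelines which visit label a suspected-progression assessment takes, in the primary and extension phases alike.

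The cost is two sentences in a SAP update, which SAP 2.10 allows before database lock. No new data are needed, since unscheduled results are already collected and listed. A table of worst post-baseline laboratory values over all visits is optional.
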